7.4.4 Description of the variables, methods and scales for their measurement

For clinical purposes, ophthalmological evaluations will be carried out in both eyes, and their record will be recorded in the clinical file. However, in order to obtain results and comply with the assumption of independence within the variables, only the examinations and qualifications of the right eye will be recorded in the eCRF when appropriate. Next, the description of the variables is made, which are not in order of execution.

7.4.4.1 Conjunctival hyperemia

It is defined as the simplest reaction of the conjunctiva to a stimulus, with a red appearance secondary to vasodilation of the conjunctival vessels of variable intensity. It will be graduated using the Efron scale. See annex [38][16.2. Efron Scale for Conjunctival Hyperemia](#)

The PI will record in the file and the eCRF the grade, in grades (Grade 0 = normal, grade 1 = traces, grade 2 = mild, grade 3 = moderate, grade 4 = severe), granted for conjunctival hyperemia OD and OS respectively.

Management as AE: An adverse event will be considered when the grade is greater than or equal to grade 3 (moderate).

7.4.4.2 Chemosis

It is defined as conjunctival edema, the result of an inflammatory reaction. It is qualified as present or absent. The evaluator will use a narrow beam of light at 60° and will measure whether the conjunctiva separates from the sclera by $\geq 1/3$ of the total eyelid opening or if it exceeds the gray line. [39]

The PI will record in the file and the eCRF if the chemosis is absent or present.

Management as AE: An adverse event will be considered when present.

7.4.4.3 Ocular symptomatology

The subject will be questioned directly about the presence in general (since the last visit) of the following symptoms: burning, foreign body sensation, pruritus, tearing.

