6.1.3 Treatment with the investigational product

The product under investigation will be delivered at the conclusion of the baseline visit. The subject under investigation will begin the application the next day (day 1) by administering one drop every 6 hours, applying a total of one drop three times a day to the right eye during the 7 days of application.

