7.4.4.3.4 Lagrimeo

Excessive tear production or flow. [35, 36]

The subject will respond only if the symptom is absent or present

These symptoms will be analyzed as one of the variables of the study and will not be considered an adverse event.

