7.4.4.5 Ocular surface staining

Fluorescein (TF) staining: A drop of topical anesthetic will be instilled in the bottom of the conjunctival sac, then a second drop will be applied to the tip of the fluorescein strip, allowing it to sit on the strip for 5 seconds to elute the dye, shaking off the excess at the end. A small contact of the strip is made with the conjunctiva at the fundus of the temporal sac, while the subject looks upwards, without damaging the conjunctiva. Between 4 and 8 minutes after the instillation of the staining, the assessment of the fluorescein stain in the cornea is carried out, with the slit lamp with a cobalt blue filter. It will be graded according to the Oxford Scale. See attachment [41, 42][16.3 Oxford scale](#)

The PI will record in the file and the eCRF the grade, in grades (Grade 0 = Absent, grade I = Minimal, grade II = Mild, grade III = Moderate, grade IV = Marked, grade V = Severe), granted for the corneal staining of OD and OS respectively.

Management as AE: An adverse event will be considered when the rating is greater than or equal to grade III (moderate).

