7.5.8.5 Gonioscopy

It is the assessment of the iridocorneal angle by attaching a gonioscopy lens to the subject's cornea. In some cases the lens will be filled with a high viscosity solution (2% hypromellose) to improve the coupling of it with the subject's cornea.

This evaluation will be carried out only at the baseline visit as part of the comprehensive ophthalmological check-up and will be useful to corroborate the subject's ophthalmological health status.

For the classification of the angle, the Shaffer system will be used.

Board 3. Shaffer's classification

DEGREE	ANGLED APERTURE	DESCRIPTION	RISK OF OCCLUDING
4	45°-35°	Open	Impossible
3	35°-20°	Open	Impossible
2	20°	Narrow	Possible
1	≤ 10°	Extremely narrow	Probable
0	0°	Closed	Occluded

Angular closure or suspected angular closure shall be considered to be Grade 2 or less in more than 180° of the angular circumference.

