7.5.9 Application of Medications During Visits

During the visits to the subjects, different medications or medical devices may be applied to the ocular surface for ophthalmological examination.

Examples:

- Tetracaine 0.5% ophthalmic solution, used to anesthetize the subject's ocular surface and facilitate the measurement of intraocular pressure, application of dyes for stains and placement of the lens for gonioscopy.
- Ophthalmic solution of tropicamide 0.8% and phenylephrine 5%, used to dilate the pupil and better assess the posterior segment.
- Hypromellose ophthalmic solution 2%, may be used by the Investigator for the assessment of gonioscopy.

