7.7.1 Baseline visit

- Signing of informed consent
- Preparation of general and ophthalmological medical history
- Pregnancy test (where applicable)
- Best-corrected visual acuity measurement
- Previous Segment Evaluation
- Fundus evaluation under pharmacologic mydriasis
- Evaluation of the angle in the anterior chamber (gonioscopy)
- Fluorescein Eye Staining
- Intraocular pressure measurement
- Evaluation of adverse events
- Eye symptoms
- Eye Comfort Index (ILO)
- Subject Code Assignment and Research Product Delivery
- Submission of the subject's diary

7.7.2 Visit 1

- Best-corrected visual acuity measurement
- Previous Segment Evaluation
- Fluorescein Eye Staining
- Intraocular pressure measurement
- Evaluation of adverse events
- Adherence Assessment
- Eye symptoms

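### The Visit 1 symptom question reaches back to the day-0 examination, before the first drop, so lasting examination discomfort enters a secondary tolerability variable in both arms

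*Combined protocol and SAP*

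**What the plan says.** **The question.** Section 7.4.4.3 says the subject is "questioned directly about the presence in general (since the last visit) of the following symptoms", followed by burning, foreign body sensation, pruritus and tearing. Section 7.4.4.3.4 fixes the answer format, "The subject will respond only if the symptom is absent or present", and the use made of it: "These symptoms will be analyzed as one of the variables of the study and will not be considered an adverse event". Table 2 (section 7.4.3) defines the variable as general presence. It assigns chi-square or Fisher tests and McNemar, the last two when applicable. Section 7.4.2.2 makes it the secondary tolerability variable.

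**Dosing.** Section 6.1.3 says: "The subject under investigation will begin the application the next day (day 1", that is, the day after the baseline visit. Section 6.1.6 says the same for the comparator.

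**The day-0 examination.** Section 7.7.1 lists "Evaluation of the angle in the anterior chamber (gonioscopy", together with fundus evaluation under mydriasis, fluorescein staining and pressure measurement. On gonioscopy, section 7.5.8.5 adds: "This evaluation will be carried out only at the baseline visit as part of the comprehensive ophthalmological check-up". For staining, section 7.4.4.5 says: "A drop of topical anesthetic will be instilled in the bottom of the conjunctival sac". Section 7.5.9 confirms that during visits "different medications or medical devices may be applied to the ocular surface for ophthalmological examination".

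**Timing and order.** Section 7.6.2 puts Visit 1 on day 3 ± 1 and the final visit on day 8. Section 7.7 leaves the order of procedures within a visit to the centre. The timeline in 7.6.2 lists eye symptoms ahead of the examinations, while 7.7.1 to 7.7.3 list them after.

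**The concern.** A tolerability question about a product should cover time on that product. At Visit 1 the recall period opens at the end of the day-0 visit and the first drop comes the next day. The period therefore begins with a drug-free stretch directly after the trial's only visit with gonioscopy.

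Gritty feeling, burning or tearing that lingers or starts after that examination is correctly answered as present. Nothing later can separate it from a product symptom. The answer has no onset date, and the symptoms are kept out of adverse event handling, so the causality assessment in section 8.5.4 does not reach them.

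Two things are at stake for this variable. The contrast between arms is diluted, and any within-arm comparison of baseline with Visit 1 can show a rise that the product did not cause. Because the order of procedures is free, the question may also be asked before the anaesthetic in one subject and after it in another.

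**Working it through.** The plan states no figure on this point, so there is none to reproduce. The check is a timeline followed by an illustration.

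**1. Timeline**
- Last visit before Visit 1: day 0 (7.6.2).
- First drop: day 1 in both arms (6.1.3, 6.1.6).
- Visit 1: day 2, 3 or 4 (3 ± 1).
- The window runs 2 to 4 days, of which up to about 1 day is before any drop: 1/4 = 25% to 1/2 = 50%.
- The final-visit window, Visit 1 to day 8, holds no pre-dose time. It does open after the Visit 1 anaesthetic, dye and tonometry.

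**2. Dilution between arms**

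Let p be the true share with a product symptom and q the share whose examination discomfort falls in the window. Assume the two are independent.
- Observed rate = 1 − (1 − p)(1 − q).
- Observed difference = (1 − q)(p_B − p_A).

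Inputs: 19 per arm (10.1.2), taking every randomised subject as analysed; two-sided 5%; p_B = 50%, the rate section 10.1.1 assumes for PRO-231; p_A = 10%, an assumption close to the 6 events in 62 patients (9.7%) quoted there. Those are adverse event figures, borrowed here because the plan gives no symptom rates. The values of q are assumptions. Fisher power is an exact enumeration of all outcomes.

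| q | Observed rates | Difference | Fisher power |
|---|---|---|---|
| 0 | 10% vs 50% | 40 points | 71% |
| 10% | 19% vs 55% | 36 points | 55% |
| 20% | 28% vs 60% | 32 points | 42% |
| 30% | 37% vs 65% | 28 points | 32% |

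Example at q = 20%: 1 − 0.9 × 0.8 = 0.28, 1 − 0.5 × 0.8 = 0.60, difference 0.32 = 0.8 × 0.40.

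With p_A = 3/62 = 4.8% (patients with at least one event in the same section), power is 88%, 69%, 54% and 41%. The pattern is the same.

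**3. False rise within an arm**

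Take 19 subjects, no product effect, an assumed 5% baseline rate, and a baseline answer free of examination effects. If baseline symptoms persist, no symptom is lost and new symptoms follow Bin(19, 0.95q). An exact two-sided McNemar test then needs at least 6 new symptoms, since 2 × 0.5⁶ = 0.031 while 2 × 0.5⁵ = 0.063.
- q = 10%: P(Bin(19, 0.095) ≥ 6) = 0.7%.
- q = 20%: P(Bin(19, 0.19) ≥ 6) = 14%.
- q = 30%: P(Bin(19, 0.285) ≥ 6) = 47%.

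If symptoms instead vary independently between visits, the chance of a new symptom is 0.95 × (0.05 + 0.95q) and of a lost one 0.05 × 0.95(1 − q). The results are then 2%, 15% and 41%.

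**The case against.** Several stronger readings are tempting, and the documents do not support them.

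- **All day-0 discomfort counts.** Read strictly, the window opens when the baseline visit ends. Sensations during the examination fall outside it, and the eye has just been anaesthetised. Only discomfort that persists or starts afterwards enters, which may mean a small q. This stands, and it is why the size is open.
- **The comparison is biased toward one product.** It is not. Allocation is randomised 1:1 (7.3) and both arms have the same day-0 examination, so the expected effect is equal.
- **Dilution produces the trial's similarity verdict.** Section 10.3.1 does read a non-significant result as similar, and 10.3.2.2 carries the same analysis to secondary variables. But section 3.2 ties the decision rule to the primary variables, and primary tolerability is the Eye Comfort Index (7.4.1.2). A diluted symptom difference does not by itself decide the trial.
- **Baseline is free of examination effects, so a rise is certain.** This is not shown. Section 7.7.1 lists symptoms after the examination and 7.7 leaves the order open. The McNemar figures apply only if the question comes first. At q = 10% the false rise is slight even then, McNemar is planned only when applicable, and no section says that a within-arm rise will be attributed to the product.
- **The final visit has the same fault.** Its window contains no pre-dose time.

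The objection does not remove the mismatch between recall window and dosing, or the fact that the recorded answer cannot be separated afterwards.

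**Conclusion.** The point holds as a measurement fault in one secondary variable at one of its two post-baseline visits. The Visit 1 answer covers time before the first drop, directly after the day-0 examination, and is stored without onset or cause. The effect is the same in both arms in expectation. It raises incidence, shrinks the between-arm difference by (1 − q), and can disturb the comparison of baseline with Visit 1.

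The direction is certain for any q above zero, but the size is not known. The power loss from 71% to between 55% and 32%, and the false rise of 0.7% to 47%, rest on an assumed q of 10 to 30%, on the assumed symptom rates and, for the false rise, on a baseline question asked before the examination. If lasting discomfort is rarer than 10%, both effects are smaller. The primary variables are untouched. The change is worth making because it costs almost nothing now, and present/absent answers without onset cannot be corrected later.

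**What to change.** - In section 7.4.4.3 and on the symptom form, ask at Visit 1 about symptoms *since your first drop on day 1*.
- In sections 7.7.1 to 7.7.3, fix the place of the question: at every visit, including baseline, it comes before any anaesthetic, dye or contact examination.
- Keep the final-visit window as it is. Starting it a day later would discard on-treatment symptoms. Optionally record onset, so that discomfort right after the Visit 1 examination can be identified.

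A fixed 3-day look-back at baseline is not part of this change, because it would not match the later windows: about 1 to 3 days from first drop to Visit 1, and 4 to 6 days from Visit 1 to day 8.

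The cost is a small change to the protocol text and form, and some loss of the centre's freedom to order procedures. No visit, subject or treatment changes.

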7.4.4.3.1 Ardent

Feeling of irritation or stinging in the eyes. [37]

7.4.4.3.2 Foreign Body Sensation

Feeling of sand inside the eye. [36]

7.4.4.3.3 Pruritus

It is an itching or tickling sensation that causes the need to rub or scratch the eye. [34]

7.4.4.3.4 Lagrimeo

Excessive tear production or flow. [35, 36]

The subject will respond only if the symptom is absent or present

These symptoms will be analyzed as one of the variables of the study and will not be considered an adverse event.

7.4.4.4 Best-corrected visual acuity

Visual acuity (VA) is a test of visual function. Visual spatial acuity is the ability to distinguish separate elements of an object and identify them as a whole. It is quantified as the minimum angle of separation (located at the nodal point of the eye) between two objects that allows them to be perceived as separate objects.

Snellen's notation is described as the distance at which the test is performed, divided by the distance at which the letter is vertically equivalent to 5 arc minutes. Thus, at 6 meters a letter 6/6 (20/20) is equivalent to 5 minutes of arc, a letter 6/12 (20/40) is equivalent to 10 minutes, and a letter 6/60 (20/200) is equivalent to 50 minutes. The Snellen fraction can also be expressed as a decimal place (i.e., 20/20 = 1 and 20/40 = 0.5). [40]

VA will be evaluated at baseline, without refractive correction with the Snellen chart (see annex [16.1 Cartilla de Snellen](#)). It will be located in a place with adequate lighting (natural or artificial) and at a distance of 3m from the subject to be evaluated. Visual acuity of the right eye (OD) will be taken initially, asking the subject to hold both eyes open and using an occluder to cover the contralateral eye; the subject will read aloud the lines that the evaluator points out, the line of smaller letters that he can see will be noted by the evaluator in fraction as the AV of OD in the clinical record and the eCRF, then the same evaluation will be performed in the left eye and its record only in the clinical file.

Next, the subject's best refractive correction (obtained by autokeratometer/refractometer and subjective tests) will be evaluated and the examination will be repeated using the refraction obtained. This result will be reported as best-corrected visual acuity.

Both data (AV and AVMC) will be reported for statistical purposes in logarithmic figures (LogMAR) in the eCRF.

A fraction conversion table is attached to LogMAR. (see annex [16.5 Fraction to LogMAR conversion table](#).)

Management as AE: A decrease in 2 or more lines of sight in BCVA compared to that obtained at baseline will be considered an adverse event.

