5.1 Eligibility Criteria

5.1.1 Inclusion criteria

- Have the ability to voluntarily give their signed informed consent.
- Ophthalmologically and clinically healthy subjects.
- Be able and willing to comply with scheduled visits, treatment plan, and other study procedures.
- Age 18 to 45 years.
- Both sexes.
- Women of childbearing potential must ensure continued use (initiated \geq 30 days prior to signing the CRF) of the use of a hormonal contraceptive method or IUD during the study period.
- AVMC of 20/30 or better in both eyes.
- Corneal staining \leq grade I on the Oxford Scale.
- Have an intraocular pressure \geq 10 and \leq 21 mmHg.

5.1.2 Exclusion criteria:

- History of hypersensitivity to fluoroquinolones or any of the components of the PI.
- Be a user of topical ophthalmic medications of any pharmacological group.
- Be a user of medicines by any other means of administration.
- History of eye surgery in the last 6 months.
- Wearing contact lenses for less than two weeks prior to the start of the study, and during the study intervention period.
- For women: being pregnant, breastfeeding, or planning to become pregnant within the study period.
- Have participated in any investigational clinical study 30 days prior to inclusion in this study.
- Have previously participated in this same study.
- History of any chronic-degenerative disease, including Diabetes Mellitus or Systemic Arterial Hypertension.
- Known diagnosis of liver or heart disease.
- Have active inflammatory or infectious disease at the time of study entry.
- Have unresolved injuries or trauma at the time of study entry.
- Having undergone surgical, non-ophthalmologic procedures within the past 3 months.
- Have received doses of vaccine against the Influenza virus or Coronavirus, 7 days prior to the inclusion of this study, or plan to receive it during the intervention of the same.

- Be or have an immediate family member (e.g., spouse, parent/legal guardian, sibling, or child) who is employed by the research site or sponsor, and who is directly involved in this study.
- Positive smoking (specified as cigarette smoking regardless of quantity and frequency, 4 weeks prior to study inclusion and during the study intervention period).
- Positive alcoholism (specified as the consumption of alcoholic beverages, regardless of quantity and frequency, 72 hours prior to the inclusion of the study and during the study intervention period).

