7.4.3 Definition of variables, methods and scales for their measurement

Board 2. Operational definition of variables

Variable	Conceptual Definition	Operational Definition	Measurement Type	Reference value	Statistical test
Incidence of Intervention-Related Unexpected AEs	Any adverse medical event that occurs in the clinical research subject to whom any of the interventions were administered and that has a certain coincidental relationship to the interventions [33]	All AEs (according to protocol) in which the PI suspects a causal relationship with the interventions will be reported	• Discrete quantitative • Nominal qualitative	• Relationship with IP • Severity • Causality	
 • Student's t-test of independent groups • U de Mann Whitney* • Pearson X² or Fisher Exact*
Incidence of conjunctival hyperemia	It is the reaction of the conjunctiva to a stimulus, a red appearance secondary to the vasodilation of the conjunctiva vessels of variable intensity is seen	Direct observation. Classification by Efron scale. See attachment 16.2. Efron Scale for Conjunctival Hyperemia	Degrees: 0 = Normal, I = Muy live, II = Mild, III = Moderate and IV = Severe		
 • Pearson X² or Fisher Exact* • McNemar Test*
Incidence of Chemosis	It is defined as conjunctival edema, the result of an inflammatory reaction. It is classified as present or absent	The evaluator will use a narrow beam of light at 60° and will measure whether the conjunctiva separates ≥ 1/3 of the total	• Nominal qualitative	Present / Absent	
 • Pearson X² or Fisher Exact* • McNemar Test*

Variable	Conceptual Definition	Operational Definition	Measurement Type	Reference value	Statistical test
Changes in the AVMC	Visual spatial acuity is the ability to distinguish separate elements of an object and identify them as a whole. It is quantified as the minimum angle of separation (located at the nodal point of the eye) between two objects that allows them to be perceived as separate objects	eyelid opening or if it exceeds the gray line Cartilla de Snellen. Ver anexo 16.5 Fraction to LogMAR conversion table.	• Continuous quantitative	20/30 (0.2 LogMAR) or better	
 • Student's t-test of independent groups • U de Mann Whitney*

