10.3.1 Population Analysis

The statistical analysis will be presented to give a general summary of the subjects entered into the study and a view of the safety and tolerability of its results. The data provided by the research site will be summarized for this purpose, according to its nature. The Shapiro-Wilk test will be performed to find out if the quantitative data are distributed in a normal way ($p>0.05$).

The results of the quantitative variables will be presented in measures of central tendency: mean, standard deviation and/or ranges. Changes in the AVMC and ICO will be expressed as continuous variables. Whereas, the incidence (number) of AEs will be expressed as a discrete variable.

The result of the nominal and ordinal qualitative variables will be presented in frequencies, proportions and/or percentages. For these, tables of frequencies $p \times q$ will be constructed. All percentages will be presented with a decimal.

The level of difference to consider significance will be an alpha (α) of 0.05 or less, the 95% CI will be calculated for these differences. The triangulation between the type of variable and the measurements is shown in Table 5. [63]

The operational definition of the study for hypothesis testing will be as follows:

Hypothesis testing	value	Result	Interpretation
P value	≤ 0.05		
95% CI	Does not include zero	H_0 rejected	Both treatments are different in terms of safety and tolerability
P value	≥ 0.05	H_0 accepted	Both treatments are similar in terms of safety and tolerability (they are not different)
95% CI	Includes zero		

Both conditions for hypothesis testing (p-value and 95% CI) must be met, otherwise the result will be interpreted as "**absence of evidence**", not as "**evidence of absence**".

Board 5. Triangulation of concepts.

Variable Type	Variable	A1	A2	B1	C1	C2	C3	C4	D1	E1	F1	F2	F3	F4
Selection														
A1	Demographic			D										
A2	Medical History/Selection Criteria				D									
Basal														
B1	Comprehensive ophthalmological evaluation			T	D	TB	TB	B	T		TB			
Primary Security														
C1	Incidence of unexpected-related AEs				TB					TB				
C2	Incidence of conjunctival hyperemia and chemosis			T		TB				TB				
C3	AVMC			B	TB			B		TB				
C4	Corneal and conjunctival stains with fluorescein			B	TB			B		TB				
Primary Tolerability														
D1	ICO								B					
Secondary Security														
E1	Incidence of AE*			T			TB							
Secondary Tolerability														

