Cuando sus ojos sentían *comezón*, por lo general, ¿qué tan intensa era la sensación?

Índice de confort ocular, traducido del Ocular Comfort Index disponible en: <http://iovs.arvojournals.org>

Hoja 2 de 2

16.5 Fraction to LogMAR conversion table.

LogMAR Value	Snellen (pies)	Snellen (metros)
1.6	20/800	20/240
1.5	20/640	6/190
1.4	20/500	6/150
1.3	20/400	6/120
1.2	20/320	6/96
1.1	20/250	6/75
1.0	20/200	6/60
0.9	20/160	6/48
0.8	20/125	6/38
0.7	20/100	6/30
0.6	20/80	6/24
0.5	20/63	6/19
0.4	20/50	6/15
0.3	20/40	6/12
0.2	20/32	6/9.5
0.1	20/25	6/7.5
0.0	20/20	6/6
-0.1	20/15	6/4.5
-0.2	20/12	6/3.6

Visual acuity equivalence table (adapted from *Ophthalmic & Physiological Optics*, 2016) [69]

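### Best-corrected visual acuity, a primary safety variable analysed as continuous, is recorded only in whole 0.1 logMAR lines, which costs precision that letter scoring would recover at almost no cost

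*Combined protocol and SAP*

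**What the plan says.** Section 7.4.1.1 lists change in BCVA (AVMC in the document) among the primary safety variables. Section 7.4.4.4 describes the reading: the subject reads lines aloud, and "the line of smaller letters that he can see will be noted by the evaluator in fraction as the AV of OD". That sentence concerns uncorrected acuity, but for BCVA "the examination will be repeated using the refraction obtained", and no other scoring rule is given. The section then states: "Both data (AV and AVMC) will be reported for statistical purposes in logarithmic figures (LogMAR) in the eCRF". The conversion table in annex 16.5 runs from 1.6 to -0.2 in steps of 0.1, with nothing in between. No credit for single letters or part lines appears anywhere.

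Entry requires "AVMC of 20/30 or better in both eyes", so baseline values can take four codes on that table (0.2, 0.1, 0.0, -0.1), or five if the chart reaches -0.2. Table 2 in section 7.4.3 classes the variable as continuous, and section 10.3.1 says "Changes in the AVMC and ICO will be expressed as continuous variables". Section 10.3.2.1 compares the arms with a t-test, or with Mann-Whitney if Shapiro-Wilk rejects normality. Large individual losses are handled separately: "A decrease in 2 or more lines of sight in BCVA compared to that obtained at baseline will be considered an adverse event".

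**The concern.** The 2-line rule already catches large losses in single subjects. What the primary comparison of change adds is the ability to see smaller average differences between arms. Whole-line recording weakens that ability most for differences below one line, because the letters that carry the information are spoken and then not written down. The arms are small, and under section 10.3.1 a non-significant result with a confidence interval that includes zero is read as similarity. Precision that could be had for nothing is therefore worth keeping.

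**Working it through.** **The plan's own figure.** The only input taken from the sample size section (10.1) is 17 evaluable subjects per arm. It reproduces with pA = 6/62 = 0.0968, pB = 0.50, two-sided alpha 0.05, 80% power (assumed; not stated) and the variance terms of both arms: (0.0874 + 0.25) × ((1.96 + 0.84)/0.403)² = 16.29, so 17. Adding 10% gives 18.7, so 19. This rests on adverse event proportions. The documents give no SD or test-retest figure for BCVA, so its variability is assumed below and shown over a range.

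**Added variance.** Rounding one reading to a step h adds about h²/12, so a change between two readings gains 2h²/12.
- Whole lines: 2 × 0.1²/12 = 0.00167.
- Letters in 0.02 steps (five per line): 2 × 0.02²/12 = 0.00007.

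With single-reading noise SD e, the variance of the unrounded change is 2e². The ratio of line to letter variance is then:
- e = 0.03: (0.0018 + 0.00167)/(0.0018 + 0.00007) = 1.86
- e = 0.05: (0.0050 + 0.00167)/(0.0050 + 0.00007) = 1.32
- e = 0.08: (0.0128 + 0.00167)/(0.0128 + 0.00007) = 1.12

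The penalty is large when readings are repeatable and small when they are not.

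**Ties at zero.** If true acuity is spread evenly within a line and there is no true change, the share of exact-zero changes is P0 = E[max(0, 1 − |D|/0.1)] with D ~ N(0, s), which equals [2Φ(a) − 1] − (2s/0.1)[φ(0) − φ(a)] with a = 0.1/s. For s = 0.05: 0.9545 − 1 × (0.3989 − 0.0540) = 0.61. Over an SD of change s of 0.03, 0.05, 0.07, 0.10 and 0.12, P0 is 76, 61, 49, 37 and 31%. It falls below one half above s of about 0.068.

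**Power.** Simulation settings: 17 per arm, true acuity N(-0.02, 0.07), a true loss of 0.05 logMAR (half a line) in one arm, Mann-Whitney at 0.05, best recordable value -0.1. Line score: ceiling to 0.1, so a line counts only if fully read (section 7.4.4.4 sets no criterion). Letter score: rounded to 0.02. Zero shares are for no true change.

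| Noise SD (assumed) | Zero changes, line | Power, line | Power, letter | Gain (points) |
|---|---|---|---|---|
| 0.03 | 68% | 65% | 88% | 23 |
| 0.04 | 58% | 50% | 66% | 16 |
| 0.05 | 51% | 39% | 48% | 9 |
| 0.06 | 45% | 29% | 35% | 6 |
| 0.08 | 36% | 19% | 23% | 4 |

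Repeat runs agree within simulation error; at noise 0.06 to 0.08 they put the gain between 2 and 6 points. Moving the limit to -0.2 changes little (64/51/39% against 88/68/48% at noise 0.03/0.04/0.05). A separate model with baseline N(-0.05, 0.08) and no limit gave 79% against 99%, 57% against 78%, 40% against 49% and 24% against 26% at an SD of change of 0.03, 0.05, 0.07 and 0.10.

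**Mean shift.** Under line scoring the true 0.05 loss appears as a mean difference of about 0.046 to 0.050. The group mean is essentially kept.

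**Which test would run.** With line scoring, Shapiro-Wilk rejects in an arm of 17 in 100, 99.8, 93 and 58% of runs at an SD of change of 0.03, 0.05, 0.07 and 0.10. Mann-Whitney with heavy ties would be the usual test.

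**The case against.** Several points on the other side stand.

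- A reader might infer that half or more of the changes must be exactly zero. The documents do not support this as a fact, because they give no BCVA variability. It is true for noise up to about 0.05 and false above it.
- A reader might infer that a loss of less than a line is largely invisible. In one eye it shows as a full line or not at all, but the arms are compared as groups, and there the mean shift survives. It would shrink materially (0.05 to about 0.03) only if readings stopped at 20/20. The documents do not say so, and annex 16.5 goes to 20/12.
- The half-line target is an assumption. The only BCVA threshold in the plan is two lines. A one-line average shift is found well by line scoring: power 99.8/97/94% at noise 0.03/0.04/0.05.
- Five letters per line and even 0.1 spacing are also assumptions. The chart in annex 16.1 is not shown, and the plan says the study chart may differ in format. With two letters per line the gain at noise 0.05 is about 38% against 45%.
- The similarity reading comes from the decision rule in section 10.3.1, not from acuity recording. Letter scoring would still miss the assumed effect 34% to 52% of the time at noise 0.04 to 0.05 (100 − 66 and 100 − 48).
- Nothing in the analysis breaks. Mann-Whitney accommodates ties.

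These points limit the size of the effect. They do not give a reason to discard the letters: letter scoring did better at every noise level examined.

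**Conclusion.** The point holds as an avoidable loss of precision in a primary safety variable. For an assumed half-line loss with 17 evaluable per arm, line scoring gives up about 23, 16 and 9 points of power at noise 0.03, 0.04 and 0.05, and only a few points at 0.06 to 0.08. The share of changes tied at zero runs from about 68% to 36% over the same range. All of this depends on the assumed noise, effect size, letters per line and line spacing, none of which the documents state. It is not an error that invalidates the comparison, and it does not hide a loss at group level. It is a cheap improvement.

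**What to change.** In section 7.4.4.4, record the number of letters read correctly on the smallest line attempted, and compute logMAR = value of that line + (step to the next larger line) × (letters missed / letters on that line), using the letter counts and line values of the chart actually used. With five letters, a 0.1 step and two misses on the 0.0 line, this gives 0.0 + 0.1 × 2/5 = 0.04. Use this value for the primary BCVA change at every visit.

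Leave the 2-line adverse event rule as written, and keep annex 16.5 for whole lines. The entry limit should be tied to the chart's own values at the same time: Table 2 gives "20/30 (0.2 LogMAR) or better", but annex 16.5 assigns 0.2 to 20/32 and has no 20/30 row. If whole-line recording is kept, describe the change as lines lost or gained on an ordinal scale and state how ties are handled.

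The cost is one extra eCRF number per reading and one scoring sentence, with the same chart, examination and visits. The interpolation is approximate where lines have few letters, and the gain is small if reading noise is large.
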